### Control Group

The control group will receive the current standard of care, which includes a resource guide with various options available to the cancer survivor. Within this guide are tips for healthy eating and pictures of standard exercises to improve fitness.

## 6.0 Procedures Involved\*

The study design is an open-label, randomized, controlled, parallel-group trial. Women age 30-80 with a recent diagnosis of stage 0, 1 or 2 breast cancer who meet inclusion and exclusion criteria will be invited to participate. As is typical and customary, a diagnosis within the last 12 weeks will be considered a recent diagnosis. Upon study enrollment and informed consent, patients will be randomly assigned to the Exercise Group or the Control Group. Random assignment will be conducted in blocks of 10 to ensure equal groups (See Appendix A). Participants will be enrolled in the study for 12 weeks.

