## **4.0 Study Endpoints\***

### Primary Study Endpoints:

- Total number of missed fractions, determined via EMR
- A break in cancer treatment, defined as missing  $\geq 3$  fractions due to patient condition, determined via EMR
- ER visits, as determined via EMR
- Inpatient and outpatient hospital encounters, as determined via EMR
- Hospital readmission for the same presenting issue, as determined via EMR
- Hospital length of stay (if hospitalized), as determined via EMR
- Cancer treatment adherence, determined via EMR
- Medications for cancer treatment symptom management, determined via EMR
- Cancer treatment-related side effects, determined via EMR
- Patient-rated pain measured by visual analog scale, as determined via EMR
- Cancer treatment tolerance, measured by the Eastern Cooperative Oncology Group (ECOG) Performance Status score, as determined via EMR
- Quality of Life, as measured by the McGill Quality of Life Measure, administered in-person at weeks 1 and 12  
[\(http://www.npcrc.org/files/news/mcgill\\_quality\\_of\\_life.pdf\)](http://www.npcrc.org/files/news/mcgill_quality_of_life.pdf)

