### Demographic and Baseline Clinical Characteristics:

- Age, as determined via electronic medical record (EMR)
- Diagnosis and diagnostic stage, as determined via EMR
- Diagnosis Date, as determined via EMR
- Body mass index, as determined by height and weight in EMR
- Comorbid chronic conditions (hypertension, diabetes, COPD), as determined via EMR
- Race/ethnicity, as determined via EMR

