## **8.0 Sharing of Results with Subjects\***

Most study parameters come from the EMR; patients have ready access to these data. The information collected outside the EMR includes quality of life (all patients) and exercise session adherence rate (Exercise Group). The Exercise Group will also receive reports on their cardiovascular, strength, and flexibility assessments.

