## **9.0 Study Timelines\***

Patient recruitment will begin after IRB approval is obtained. Each patient will be enrolled in the study for 12 weeks. Study enrollment is expected to take place over approximately 6 months, until 70 patients are enrolled. When 70 patients have been enrolled, enrollment will close, and active subjects will be followed for the remainder of their 12 week participation. Once all patients have completed the study, data will be abstracted from the EMR and analyzed within 12 months.

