## **10.0 Inclusion and Exclusion Criteria\***

Patients will be selected according to the Consolidated Standard of Reporting Trials criteria. Criteria not determined via EMR are determined via the form in Appendix B. Inclusion criteria are:

- Female; determined from electronic medical record
- Initial stage 0, 1 or 2 breast cancer diagnosis within the past 12 weeks determined from electronic medical record
- Age 30-80; determined from electronic medical record
- Physician clearance to participate in exercise

Exclusion criteria are:

- Participation in supervised physical exercise within 6 months prior to study enrollment
- Currently pregnant or planning to become pregnant
- Non-English speaking
- Unable to make own medical decisions and/or to follow verbal instructions

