## **17.0 Data Management\* and Confidentiality**

### Data Management:

All study parameters from the EMR will be downloaded by an EMR specialist via a report, de-identified, and housed in a Microsoft Excel database. Patient forms, including consent forms, will be stored in a locked file cabinet at Maple Tree Cancer Alliance. All patients will be assigned a Study ID number and a list linking patient names to Study ID number will be kept separately from the study data, on a password-protected computer. Data from patient forms will be entered into the master Microsoft Excel spreadsheet. Only Study ID will be used to identify patients in the spreadsheet.

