**Appendix A: Randomization Scheme using Block Size of 10**

Subject	Study Group Assignment
1	Control
2	Exercise
3	Exercise
4	Exercise
5	Control
6	Control
7	Control
8	Control
9	Exercise
10	Exercise
11	Exercise
12	Control
13	Control
14	Control
15	Exercise
16	Exercise
17	Control
18	Control
19	Exercise
20	Exercise
21	Control
22	Exercise
23	Exercise
24	Control
25	Exercise
26	Exercise
27	Control
28	Control
29	Exercise
30	Control
31	Exercise
32	Exercise
33	Control
34	Control
35	Exercise
36	Control
37	Control
38	Exercise
39	Exercise
40	Control
41	Exercise
42	Control

PROTOCOL TITLE: Randomized, Controlled Trial of an Individualized Exercise Oncology Program for Newly Diagnosed Breast Cancer Patients

43	Exercise
44	Exercise
45	Exercise
46	Control
47	Control
48	Exercise
49	Control
50	Control
51	Exercise
52	Exercise
53	Exercise
54	Control
55	Control
56	Control
57	Control
58	Exercise
59	Exercise
60	Control
61	Control
62	Control
63	Exercise
64	Exercise
65	Control
66	Exercise
67	Control
68	Exercise
69	Exercise
70	Control

PROTOCOL TITLE: Randomized, Controlled Trial of an Individualized Exercise Oncology Program for Newly Diagnosed Breast Cancer Patients

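### The full 70-patient allocation list is printed in the protocol of an open-label trial, and no concealment is described

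*Combined protocol and SAP*

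**What the plan says.** Section 6.0 describes an open-label, parallel-group trial in which assignment follows enrolment and consent: "Random assignment will be conducted in blocks of 10 to ensure equal groups (See Appendix A". The list is headed "Appendix A: Randomization Scheme using Block Size of 10" and gives a named group for every subject from 1 to 70. Section 12.0 sets the sample at 70, 35 per group.

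The steps before assignment are described, with the people who carry them out:

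- **Approach:** the research coordinator identifies patients at tumor conferences and seeks physician approval (Section 13.0).
- **Eligibility:** a research intern of the organization that delivers the exercise completes the form (Appendix B).
- **Consent:** a research intern of that organization conducts it. Patients may take the form home and phone in a decision (Section 22.0).

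The only access control is in Section 17.0: "a list linking patient names to Study ID number will be kept separately from the study data, on a password-protected computer". That covers the link between names and Study IDs, not the allocation list. Appendix C pre-numbers Study IDs 1, 2, 3 and so on, gives none to excluded patients, and has a column for the assignment. Section 15.0 says patients and treating physicians will know the group.

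**The concern.** Consent before assignment protects a randomized comparison only if the people deciding whom to enrol, and when, cannot know the next group. Here the sequence is part of the protocol. Someone who knew that Exercise came next could, even without intending it, bring forward a fitter or more motivated patient and hold back another. The group difference would then partly reflect who was enrolled.

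Several primary endpoints are exposed to this. A treatment break is defined in Section 4.0 by reference to the patient's condition. That pain, performance status and quality of life also depend on baseline condition is a reasonable inference.

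The analysis would not reliably repair it. The Data Analysis Plan in Section 17.0 adjusts only for baseline differences that reach statistical significance. The baseline list in Section 4.0 includes stage, body mass index and "Comorbid chronic conditions (hypertension, diabetes, COPD), as determined via EMR", but no baseline pain, performance status or fitness. Quality of life is "Quality of Life, as measured by the McGill Quality of Life Measure, administered in-person at weeks 1 and 12", and Section 8.0 confirms it is collected in both groups, but the week 1 value is not listed as a baseline covariate.

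**Working it through.** **1. Is Appendix A the complete list?** Transcribed in blocks of 10 (C = Control, E = Exercise):

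| Block | Sequence | E:C | Certain from earlier assignments |
|---|---|---|---|
| 1 | CEEECCCCEE | 5:5 | 2 |
| 2 | ECCCEECCEE | 5:5 | 2 |
| 3 | CEECEECCEC | 5:5 | 1 |
| 4 | EECCECCEEC | 5:5 | 1 |
| 5 | ECEEECCECC | 5:5 | 2 |
| 6 | EEECCCCEEC | 5:5 | 1 |
| 7 | CCEECECEEC | 5:5 | 1 |

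The total is 70, split 35:35, which reproduces Section 12.0. This is the full list, not an example.

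**2. How much can be predicted?**
- With the list and the enrolment count, if subject number follows enrolment order: 70/70.
- Without the list, but knowing the block size and every earlier assignment: 2+2+1+1+2+1+1 = 10 of 70 are certain. Guessing the group with more places left in the block is right 35 times and wrong 12 times, with 23 ties. Counting ties as half gives 35 + 11.5 = 46.5, and 46.5/70 = 66%, against 50% by chance.

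**3. Is there room to reorder patients?** Section 9.0: "Study enrollment is expected to take place over approximately 6 months, until 70 patients are enrolled". That is 70/26 = 2.69 per week. The longest run of one group is 4, and 4/2.69 = 1.5 weeks, about 10 days. Section 10.0 requires "Initial stage 0, 1 or 2 breast cancer diagnosis within the past 12 weeks determined from electronic medical record", so the window prevents waiting for the other group mainly for patients near its end.

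**4. What would steering do to the false-positive rate?** The documents give no steering size or event rates, so these are assumed ranges. Each patient is shifted by s SD in the direction of the next group, so the groups differ by δ = 2s with no treatment effect. There are 35 per group and the test is two-sided at 5%.

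- *t-test:* noncentral t, df 68, noncentrality δ√(35/2). For δ = 0.1, 0.2, 0.4 this is 0.418, 0.837, 1.673.
- *Chi-square:* exact enumeration, with event probabilities Φ(Φ⁻¹(p) ∓ δ/2). For p = 10% and δ = 0.4 these are 6.9% and 14.0%.
- *Mann-Whitney:* tie-corrected, 20,000 simulations. Counts have 70–90% zeros and geometric non-zero values (p = 0.4). Three-level performance status has level splits 80/15/5, 60/30/10 and 50/40/10.

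| Endpoint type | No steering | s = 0.1 (δ = 0.2) | s = 0.2 (δ = 0.4) |
|---|---|---|---|
| Yes/no, 5/10/15/20% events | 3.6/5.7/5.3/4.9% | 5.2/8.6/8.7/8.7% | 10.0/17.2/19.2/20.6% |
| Counts, 70/80/90% zeros | about 5% | 10.0/9.2/7.3% | 26.0/22.1/16.1% |
| Three-level ordinal | about 5% | 9.2/10.8/11.1% | 20.9/27.6/29.9% |
| Normal (upper illustration) | 5% | 13.1% | 37.8% |

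At s = 0.05 the normal case gives 7.0%. If the list is used for half the patients, δ halves, so the last column falls to about the one before it. Steering by block guessing alone separates the groups by (35 − 12)/35 = 0.657 times s. For a normal outcome that gives 5.8% at s = 0.1 and 8.4% at s = 0.2.

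**5. Would the baseline check catch it?** The same t-test calculation applies to a single normally distributed covariate. A shift of 0.2 SD between groups is significant 13% of the time, and 0.4 SD 38% of the time.

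**The case against.** The strongest reply is that harm needs three things the documents do not show: subject number follows enrolment order, someone who recruits has the list open, and that person uses it. This stands. The point is a risk, not evidence that bias occurred. The sequential Study IDs in Appendix C do support the first step, and the protocol gives no other rule for using the list.

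The full-steering rates are also demanding. Physicians control approach and clearance, sex, age, stage and diagnosis date are checked against the medical record, and a patient who takes the consent form home partly sets her own timing. Steering all 70 patients would need a steady queue of candidates. The half-use figures are therefore the more realistic guide, and at 0.1 SD each way the effect on yes/no endpoints is modest (5–9%, against 4–6% with none).

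Appendix C logs everyone assessed, with reasons for exclusion. That makes selective exclusion partly traceable, but it conceals nothing and would not show a change in the order of enrolment.

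The block-guessing figures need knowledge of all earlier assignments across two centers, which nobody is shown to have. The flagging rates in step 5 are for one covariate, while the plan lists several.

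The order of steps in Section 6.0 is not an answer: placing assignment after consent does not hide a printed sequence.

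**Conclusion.** The concern holds and should be fixed before any further enrolment. It is certain from the documents that the operative sequence is printed in full and that no custody, access rule or release procedure is given for it. That all 70 assignments are readable in advance is conditional on subject number following enrolment order.

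The effect on the results cannot be fixed from the documents. Under the assumptions above, false-positive rates run from barely above nominal to about 30% for the yes/no, count and ordinal endpoints, and to 38% for a normally distributed outcome under full steering at 0.2 SD. The case for change does not depend on any one of these figures. Selection at enrolment cannot be undone in the analysis, and as written the sponsor could not show afterwards that it did not happen.

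**What to change.** **Essential**
- Void Appendix A and remove the sequence from the protocol, keeping only the method.
- Generate a new list for the patients still to be enrolled.
- Name an existing person outside recruitment, consent and exercise delivery to hold it. Alternatively, have such a person prepare sequentially numbered, sealed, opaque envelopes, and state who keeps them at each center and how each opening is logged.
- Release an assignment only when eligibility and consent are complete and the Study ID is logged.
- If enrolment has begun, report the change and how many patients were assigned under each list.

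**Optional:** do not disclose the block size, vary it, and keep the list away from the staff who extract the medical-record data.

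**Cost:** a short amendment and, by my estimate, a few hours of preparation, with no extra patients or visits. Switching in mid-block can leave the groups slightly unequal. The largest running imbalance in Appendix A is 3, and an odd number of remaining patients adds 1, so the worst final split is 37 vs 33 if the new list is balanced over those remaining. Switching at a multiple of 10 keeps 35 vs 35.

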## **7.0 Data and Specimen Banking\***

N/A

## **8.0 Sharing of Results with Subjects\***

Most study parameters come from the EMR; patients have ready access to these data. The information collected outside the EMR includes quality of life (all patients) and exercise session adherence rate (Exercise Group). The Exercise Group will also receive reports on their cardiovascular, strength, and flexibility assessments.

## **9.0 Study Timelines\***

Patient recruitment will begin after IRB approval is obtained. Each patient will be enrolled in the study for 12 weeks. Study enrollment is expected to take place over approximately 6 months, until 70 patients are enrolled. When 70 patients have been enrolled, enrollment will close, and active subjects will be followed for the remainder of their 12 week participation. Once all patients have completed the study, data will be abstracted from the EMR and analyzed within 12 months.

## **10.0 Inclusion and Exclusion Criteria\***

Patients will be selected according to the Consolidated Standard of Reporting Trials criteria. Criteria not determined via EMR are determined via the form in Appendix B. Inclusion criteria are:

- Female; determined from electronic medical record
- Initial stage 0, 1 or 2 breast cancer diagnosis within the past 12 weeks determined from electronic medical record
- Age 30-80; determined from electronic medical record
- Physician clearance to participate in exercise

Exclusion criteria are:

- Participation in supervised physical exercise within 6 months prior to study enrollment
- Currently pregnant or planning to become pregnant
- Non-English speaking
- Unable to make own medical decisions and/or to follow verbal instructions

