## 2.0 Objectives\*

The primary objective is to test the effect of an individualized exercise oncology program on healthcare utilization, 30-day hospital readmission, pain, and cancer treatment tolerance.

H1: Among women newly diagnosed with stage 0, 1 or 2 breast cancer, those enrolled in an individualized exercise oncology program will have fewer emergency room (ER) visits, fewer hospital encounters, fewer 30-day hospital readmissions, fewer breaks in cancer treatment, less pain, and better cancer treatment tolerance than those in the control group over 3 months.

The secondary objective is to examine the feasibility of an individualized exercise oncology program via adherence and attrition rates.

H2: Among women newly diagnosed with stage 0, 1 or 2 breast cancer and enrolled in an individualized exercise oncology program, adherence to scheduled exercise sessions will average 70% or more, and program attrition will average 70% or less over 3 months.

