## 3.0 Background\*

In 2018, it was estimated that there were 1.7 million new cancer diagnoses in the U.S. For all types of cancer, mortality rates are on the decline, and patients are living longer with the chronic and late effects of treatment. This often results in costly hospital readmissions and emergency department (ED) visits, leading to increased costs, lowered health outcomes, and lengthened stays for patients.

Several meta-analyses report that exercise interventions are beneficial for patients undergoing cancer treatment, in that they reduce symptom severity and improve cancer-related fatigue, cardiac function, muscle weakness, and overall quality of life. Yet, it still remains that less than 5% of patients are ever referred to an exercise oncology program during treatment. Therefore, economic evaluations of exercise oncology are warranted, in attempt to evaluate the integration of exercise oncology as a standard part of clinical practice.

Maple Tree Cancer Alliance has developed an oncology exercise program, which results in improved health outcomes, and also cost-saving for facilities and payers. Our retrospective data demonstrated that individualized exercise during cancer treatment significantly reduced ED visits, 30-day readmissions, and length of hospital stays resulting in a payer benefit of \$3,000/patient over the first 6 months of enrollment into the Maple Tree Exercise Oncology program^2. As a follow up to this research, the purpose of the present study is to prospectively analyze the cost savings of an individualized exercise oncology program when under a rigorous, randomized, controlled design. We hypothesize that

**PROTOCOL TITLE:** Randomized, Controlled Trial of an Individualized Exercise Oncology Program for Newly Diagnosed Breast Cancer Patients

individualized exercise training during cancer treatment will improve treatment outcome, lending to a decrease in healthcare-related expenditure.

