## 5.0 Study Intervention/Investigational Agent

### Exercise Group

The study intervention is a supervised, individualized exercise oncology program described in previous literature and provided by Maple Tree Cancer Alliance, a non-profit organization providing exercise training to individuals with cancer (<https://www.mapletreecanceralliance.org/>). This organization was founded in 2011 and currently operates in 9 hospitals serving Ohio and Pennsylvania, offering free exercise programs and nutritional guidance to approximately 500 patients annually to help relieve side effects related to cancer treatment.

Patients in the supervised, individualized exercise oncology program (Exercise Group) will complete a 60-minute exercise session once per week for 12 weeks at Maple Tree Cancer Alliance. The exercise sessions will be individualized to the patient's needs and fitness level by a trainer with a bachelor's degree in exercise science and a national certification for exercise oncology. A patient will work with the same trainer throughout the study, who will plan the patient's individualized exercise regimen, and who will provide one-on-one supervision for the duration of each 60-minute session. Each 60-minute session will include cardiovascular, strength, and flexibility training.

Cardiovascular exercise will be performed on a treadmill. The intensity level for the aerobic exercise ranges from 30-45% of the individual's predicted VO2max, controlled by heart monitors (model S810i; Polar Electro) and lasting 30 min. Strength training will involve a full body workout, with emphasis on all major muscle groups and employing machines, free weights, and resistance tubing. Patients will complete 3 sets of 10 repetitions for each strength exercise. Flexibility training will involve static stretching of all major muscle groups for 15-20 seconds at the completion of each workout.

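### Entry and the 12-week period are not tied to cancer treatment, so patients with no fractions scheduled in their window dilute the missed-fraction and treatment-break comparisons

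*Combined protocol and SAP*

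**What the plan says.** **Entry.** Section 10.0 requires "Initial stage 0, 1 or 2 breast cancer diagnosis within the past 12 weeks determined from electronic medical record", together with female sex, age 30-80 and physician clearance for exercise. Section 6.0 gives the same time limit: "a diagnosis within the last 12 weeks will be considered a recent diagnosis". Neither section mentions treatment that is planned, started or finished, and the eligibility form in Appendix B has no treatment item.

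**Clock.** Section 6.0 places randomisation at enrolment: "Upon study enrollment and informed consent, patients will be randomly assigned to the Exercise Group or the Control Group". Section 9.0 adds: "Each patient will be enrolled in the study for 12 weeks". In Section 5.0, Exercise Group patients "will complete a 60-minute exercise session once per week for 12 weeks at Maple Tree Cancer Alliance". Section 24.0 states that treatment decisions do not depend on study participation, so the study does not set treatment timing either.

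**Question asked.** The Background (Section 3.0) hypothesises that "individualized exercise training during cancer treatment will improve treatment outcome". H1 in Section 2.0 predicts, among other things, "fewer breaks in cancer treatment, less pain, and better cancer treatment tolerance than those in the control group over 3 months".

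**Endpoints and analysis.** The primary endpoints in Section 4.0 include the number of missed fractions, a break of 3 or more missed fractions, treatment adherence, treatment side effects and symptom medication. They also include ER visits, hospital encounters, pain, ECOG status and quality of life. Section 12.0 bases the 70 subjects on missed fractions. The baseline list in Section 4.0 has the diagnosis date but no treatment modality, start date or end date. The analysis plan in Section 17.0 has no rule for a patient with no fractions scheduled in her 12 weeks.

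**The concern.** A patient may enrol at any time from 0 to 12 weeks after diagnosis, so one patient is observed in weeks 0-12 after diagnosis and another in weeks 12-24. A patient whose radiation ended before enrolment meets every criterion. So does one whose radiation starts after her week 12. Either would have no missed fraction and no break in the window, whichever arm she is in.

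Such patients carry no information on these two endpoints, yet nothing removes them from the comparison. They shrink the mean difference, and with it the power of the endpoint that justifies the sample size. If the result is null, the reader cannot tell an ineffective programme from 12 weeks in which many patients had no fractions to miss. Because modality and planned dates are not baseline items, the plan provides no pre-randomisation data from which to separate the two afterwards.

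**Working it through.** **Inputs from the documents.** 35 per arm and 80% power for a medium effect in missed fractions (Section 12.0); two-sided alpha .05 (Section 17.0).

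**Inputs assumed, because the documents do not give them.** The share f of patients with fractions scheduled in the window; mean 2 and SD 2 missed fractions among control patients with fractions, with SD 2 in the exercise arm too; a score of zero for patients without fractions. Section 17.0 does not state a scoring rule, but a count of zero is what an EMR download would return.

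**1. The plan's own figure.** The plan puts no number on a medium effect. If it means d = 0.5, a two-sided t-test needs 64 per arm, and 35 per arm gives 54% power, so the stated 80% is not reproduced. The effect for which 35 per arm gives 80% is d = 0.68. That shortfall is a separate matter. I start from d = 0.68 so that power is 80% when f = 1 and any loss below comes from dilution alone.

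**2. Dilution.** With d = 0.68 and SD 2, the exercise mean among patients with fractions is 2 - 0.68 × 2 = 0.64. If a share 1 - f of each arm scores zero:

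- mean difference = f × (2 - 0.64) = 1.36f
- variance in an arm with mean m = f(SD² + m²) - (fm)²
- diluted d = 1.36f / √(average of the two arm variances)

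At f = 0.75:
- control variance = 0.75 × 8 - 1.5² = 3.75
- exercise variance = 0.75 × 4.4096 - 0.48² = 3.08
- pooled SD = 1.85, so d = 1.02 / 1.85 = 0.55

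At f = 0.50:
- control variance = 0.50 × 8 - 1² = 3.00
- exercise variance = 0.50 × 4.4096 - 0.32² = 2.10
- pooled SD = 1.60, so d = 0.68 / 1.60 = 0.43

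**3. Power** (noncentral t, two-sided .05):

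| Share with fractions in window | All 35 per arm, others scored zero | Only patients with planned fractions (35f per arm, d = 0.68) |
|---|---|---|
| 100% | 80% | 80% |
| 75% | 62% | about 68% (26.25 per arm) |
| 50% | 42% | about 50% (17.5 per arm) |

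**4. Sensitivity to the model.** If the SD is held fixed and the effect simply becomes f × d, power at f = 0.50 is 29% instead of 42%. The direction is the same in both models; the size is not well determined.

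**5. Can f be derived from the plan?** No. Suppose enrolment is uniform over 0-12 weeks from diagnosis and a radiation course lasts 5 weeks. The share of patients with no part of the course in their window is then 8% if radiation starts at week 6 after diagnosis, 0% for starts at weeks 8 to 12, 33% at week 16, and 100% at week 24 or later. The documents give neither start weeks nor course length, so any value of f is an assumption.

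**The case against.** The strongest reply is that the plan's formal hypothesis concerns newly diagnosed women compared over 3 months, and that entry by diagnosis date fits that population. The wording about exercise during treatment is in the Background. This stands to a considerable extent. ER visits, hospital encounters, pain, ECOG and quality of life can be compared in every patient whatever her treatment timing. A reader might infer that the trial cannot answer its question at all, and the documents do not support that. H1 does, however, include treatment breaks, and Section 12.0 rests on missed fractions, so the point remains for those endpoints.

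A reader might also infer that every treatment-related endpoint fails in the same way. It does not. A patient on systemic treatment during her 12 weeks, with radiation later, can still show effects on adherence, side effects and symptom medication. Those endpoints lose information only from patients with no treatment of any kind in the window.

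A third inference would be that unbalanced treatment timing biases the comparison. Randomisation balances timing on average, and chance imbalance is already covered by the 5% error rate.

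Finally, the recruitment routes in Section 13.0 (tumor conferences, the initial information packet, the Breast Cancer Class) suggest early enrolment. That makes patients who have already finished radiation less likely, but does nothing for radiation that starts late. The objection that the magnitudes are assumed is correct. They show how the loss behaves and do not estimate it.

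**Conclusion.** The point holds for the missed-fraction and treatment-break endpoints. Neither entry nor the 12-week period is tied to treatment, modality and dates are not collected at baseline, and the analysis plan has no rule for patients without scheduled fractions. The consequence is lost power and a null result that is hard to read, not systematic bias. Its size is unknown: power would fall from 80% to 62% or 42% if 75% or 50% of patients had fractions in the window, given d = 0.68 among those patients, an assumed control mean and SD of 2, and zero scores for the rest. The same arithmetic applies to a patient who never receives radiation, so it measures the absence of fractions from the window whatever the reason. The gap can be closed cheaply and is worth closing, but it does not invalidate the remaining comparisons.

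**What to change.** - **Section 4.0, baseline characteristics:** add planned treatment modality and planned start and end dates, taken from the EMR before randomisation.
- **Section 17.0, analysis plan:** analyse missed fractions and treatment breaks in patients with fractions planned within weeks 1-12. Analyse adherence, side effects and symptom medication in patients with any cancer treatment planned within weeks 1-12. Define both sets only from data recorded before randomisation, so that the randomised comparison is kept within each. Keep all randomised patients for the remaining endpoints.

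The cost is a few extra EMR fields and a smaller analysis set for the treatment endpoints. The change recovers only part of the lost power (about 68% against 62%, and 50% against 42%, in the illustration), but it makes the result interpretable. The planned dates have to be captured prospectively, so the change is best made before enrolment proceeds.

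Restricting eligibility to patients with planned treatment, or starting the 12 weeks at treatment start, is a design option for the sponsor and not a required correction. Either could slow accrual, and moving the clock could change when exercise begins. A criterion met by either radiation or systemic treatment would still admit patients with no fractions.
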